14 STATISTICAL ANALYSES

Calculation of number of participants needed

We will use a pragmatic approach with the objective to recruit the maximum of MSM and TGW. According to the IBBS 2019, the estimated number of MSM in Phnom Penh is 6300 and the

Version 1.1 du 18/04/2022

estimated number of TGW is 1400.

With 1500 participants (1000 MSM and 500 TGW), we will be able to estimate an HIV self-test uptake of 70% to within a 95% confidence interval of +/- 2 – 2.5% (width of the confidence interval (in %) = $1.96 \times \sqrt{(p \times (1-p)/n)}$.

Analysis plan

Description of the characteristics at inclusion.

These variables will be described by their median, interquartile range, mean, standard deviation, or frequencies (%), as appropriate. These variables will be compared to those reported in the IBBS 2019 for MSM and TGW.

Primary outcome

The percentage, and its 95% confidence interval of HIV self-tests delivered among the total number of coupons distributed will be given and stratified by gender (MSM or TGW) and by type of coupons (paper or electronic).

Secondary outcomes

- The percentage and its 95% confidence interval of HIVST result's recorded among the total number of HIVST delivered will be given and stratified by gender (MSM or TGW)
- For those accepting to be contacted by phone, the percentage and its 95% confidence interval of HIVST realized among the number of HIV tests results non recorded will be given
- The percentage and its 95% confidence interval of participants with positive HIV selftests linked to an ART site will be given and stratified by gender (MSM or TGW)
- The percentage and its 95% confidence interval of participants with negative HIV selftests linked to PrEP services will be given and stratified by gender (MSM or TGW)
- The percentage and its 95% confidence interval of participants with 6-monthly repeated HIV testing during the 18 months (so 4 HIVSTs during the total duration of the study) will be given
- The probability of discontinuation of HIV testing and its 95% confidence interval, as well as the median time to the occurrence of HIV testing discontinuation, will be determined using a Kaplan Meier analysis, to take into account censored data due to lost of follow-up.

For qualitative assessment, bilingual research staff transcribed all interviews verbatim and translated them into English. We used both inductive and deductive approaches when analysing the data. Inductive analysis was used in the early stage to explore the ideas and meanings contained in the raw data and to identify concepts, patterns and themes. Similar codes were collated to form initial themes. Once patterns, themes and subthemes were established by open coding, deductive content analysis was used to validate these in an iterative process. We reported the results in participant-based, and provider-based issues. QSR NVivo V.12 for Windows was used to manage the data.

Version 1.1 du 18/04/2022

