These recruited individuals will be considered as wave 1 of recruitment and will each receive 10 additional coupons to recruit the members of their networks. The next round of individuals recruited and enrolled will be considered as wave 2, and so on. The number of 10 coupons was selected to avoid a bias risk related to participation incentives.

To facilitate the return of HIVST kit results, participant will upload the picture of results labeled with their identifier directly using the link of the external website that they received from community worker/research team during their visits at pharmacy. In case of any question, they could reach community worker/research team by hotline number. According to the results, the participants will be proposed with a support for linkage to confirmatory test or to PrEP services. Each non-reactive participant will be provided another new coupon (paper or electronic format upon their preference) with a reminder to perform a 6-monthly HIV testing during 18 months. They will not be granted any token or incentives if they fail to return the result of HIVST kit taken at pharmacies. These incentives are also added upon the number of recruited members of their networks using common money transfer and payment services in Cambodia such as Wing, TrueMoney.

After 6 months, a qualitative assessment will be conducted to evaluate feasibility, acceptability and appropriateness of the intervention and to identify barriers and facilitators.

Several ART sites/HIV clinics particularly in charge of key populations will be specifically selected as participating centers in order to collect information on linkage to care or prevention services for positive and negative participants, respectively.

Tentative study agenda

- Protocol submission: December 2022
- Study implementation: February 2023 July 2023
- Data collection: August 2023 April 2025 (18 months)
- Duration of the study: 24 months

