7 STUDY ENDPOINTS

Primary endpoint

 HIV self-testing uptake defined as the number of HIV self-tests delivered / total number of coupons distributed

Secondary endpoints

- Proportion of HIVST result's recorded / total number of HIVST delivered
- Proportion of paper and electronic coupons delivered
- Number of HIV tests realized / number of HIV tests results non recorded
- Proportion of MSM/TGW with positive HIV self-tests linked to an ART site
- Proportion of negative MSM/TGW linked to PrEP services
- Characteristics of participants recruited (sociodemographic, sexual behavior, utilization of dating application, substance use) in comparison with IBBS 2019 report
- Proportion of participants with 6-monthly repeated HIV testing during 18 months

Outcomes of acceptability and appropriateness will be explored during focus groups: comfort, usefulness, suitability, confidentiality, credibility, advantages and barriers.

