Incentives will be provided in two steps for participants to encourage them to return the results of HIVST and recruit their peers. In step one, each participant will receive 2 USD for returning the HIVST result successfully to the provided link. In step two, an amount of 1 USD will be provided for each recruited peer. This amount was decided as a balance between feasibility (encouragement) and sustainability of the strategy (not too high for possible scaling-up).

In case of any issue for tablet use or HIVST kit use, helpline phone number will be available. One dedicated community worker funded by the study will be in charge to manage helpline service.

Intervention after delivering HIV test result

In case of reactive HIV test, the participant could join immediately one research team by hotline or messages on the website that will provide support and orientation. After 1 week, contact with the participant will be done by phone by the research team (if the participant gave consent) to confirm the linkage to one of the partner ART sites. The linkage between participants and HIV clinics will be done by the initial QR code.

Version 1.1 du 18/04/2022

If the linkage to confirmatory testing and/or care is not confirmed, we will propose to participant additional help of a community worker.

In case of non-reactive test, the participant could download in the external website one electronic coupon (QR code) to repeat the HIV test 6 month later. Participants will be informed on the external website about the possibilities to join the pilot PrEP program in Chhouk Sar clinic in Phnom Penh.

Qualitative assessment

After 6 months, a qualitative assessment will be conducted to evaluate acceptability and appropriateness of the intervention. Qualitative assessment will be done by focus groups. Focus groups will be conducted in 3 specific populations: MSM, TGW and pharmacists. For each population of MSM and TGW, a qualitative sample will be selected in order to capture different profiles according to sex behaviors and demographic and socioeconomic characteristics.

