Participation to focus groups will be anonymous and voluntary. Participants will be recruited via the interview in the pharmacy and by the external website. Focus groups will be conducted in a dedicated room, facilitated by a researcher in social and human sciences with the help of the project manager, trained to focus groups and using grids describing topics. Each focus group will be composed of 9-10 members for a 60-90 minutes discussion that will be recorded to facilitate retranscription and translation. Records will be deleted at the end of the study.

The topics included in grids for focus groups with MSM and TGW will be:

- Acceptability of the HIV test delivery: confidence and confidentiality, non-judgmental attitude, quality of explanations, location of pharmacies
- Acceptability of the HIV self-testing realization: quality of information and useinstructions, painful or stress experience, solitude feeling, orientation after testing
- Appropriateness of the strategy: usefulness, perception and improvement of the strategy, willingness to repeat the test in 6 months

The topics included in grids for focus groups with pharmacists will be:

- Satisfaction of the HIV test delivery: feeling at ease, time-consuming, contact with participants, logistical issues
- Willingness to sustain the strategy, perception and improvement of the strategy

Withdrawal of consent and loss to follow-up

Consent withdrawal

A participant will be considered to have withdrawn consent if s/he no longer wishes to remain in the study. In this case, a "withdrawal of consent form" could be filled in the external website.

When a participant who withdraws consent explicitly expresses the will that his/her data be removed from the database and his/her laboratory samples be destroyed, the study team will

Version 1.1 du 18/04/2022

carry out such will. When a patient who withdraws consent do not express such will, data and samples collected prior to the date of his/her consent withdrawal will be used for the analysis.

Loss to follow-up

When a participant who has not explicitly withdrawn consent does not return the HIVST result after one week, the research team will reach them by phone. Also, 1 week after returning positive HIVST results, if there is no information confirming the linkage to one of the partner ART sites or participant does not show up after receiving the reminder for 6-month HIVST, the research team will reach them by phone.

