Essential study documents (protocol, case report forms, SOPs, etc) and regulatory (ethical clearance, task delegation, agreements, curriculum vitae, etc..) will constitute the Trial Master File (TMF). The TMF will be held at the GMO located at the UHS and will be retained for 15 years.

Each investigator will keep a hard copy of relevant TMF documents in an Investigator Site File (ISF). The Clinical Research Assistants (CRAs) will be responsible for checking that the documents contained in the ISF of each study site are up-to-date.

Data management

The UHS Team will be responsible, on behalf of the sponsor, for implementation of procedures for data collection, storage, protection, retention and destruction. The team has implemented a data safety and security concept according to the requirements. All related procedures will be developed in cooperation with the data security engineer of the UHS team and have to be approved by the official data protection officer of the University of Health Sciences prior to implementation.

Version 1.1 du 18/04/2022

Data collection

Data from participants will be collected in partner pharmacies, after signature of Informed consent, in tablets on electronic case report forms (e-CRF). The community workers will be responsible for filling out data into the e-CRF. A unique e-CRF will be assigned for each participant. The participant will only be registered through a unique confidential code. A Standard Operating Procedure (SOP) will be provided to guide the community workers to fill out the e-CRF. All information required by the protocol should be provided and any omission would require explanation.

The CRAs are responsible for ensuring that all sections in the e-CRF are completed correctly and that number of entries can be verified with the number of HIVST delivered in each pharmacy. The results of the HIVST will be recorded by the participants on the external website with the unique ID.

Data entry and checking

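### Linkage to ART can be measured only among participants whose positive result becomes known to the study, so the percentage is likely, though not certainly, overstated

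*Protocol*

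**What the plan says.** Section 7 of the protocol lists the endpoint as "Proportion of MSM/TGW with positive HIV self-tests linked to an ART site". Section 14 says that the percentage and its 95% confidence interval "of participants with positive HIV selftests linked to an ART site will be given and stratified by gender". Neither place says what makes a self-test count as positive, or how a delivered kit with no result is treated.

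On recording, section 13 (Data collection) says: "The results of the HIVST will be recorded by the participants on the external website with the unique ID". Section 5 describes the same route, a photograph of the result uploaded by the participant. Incomplete return is expected, because another secondary endpoint in section 7 is "Proportion of HIVST result's recorded / total number of HIVST delivered".

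The protocol gives three further ways in which a reactive result could become known:
- **Hotline or message.** Section 9 says: "In case of reactive HIV test, the participant could join immediately one research team by hotline or messages on the website".
- **Phone call.** Section 9 (Loss to follow-up) says that when a participant "does not return the HIVST result after one week, the research team will reach them by phone". Recontact by phone is one of the separate consents in section 9.
- **Clinic match.** Sections 8 and 9 link participants to the HIV clinics by the initial QR code.

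The only planned analysis of the calls to non-returners is in section 14: "For those accepting to be contacted by phone, the percentage and its 95% confidence interval of HIVST realized among the number of HIV tests results" that were not recorded. It concerns whether the test was done. Neither section mentions asking for the result.

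**The concern.** The objective in section 4 concerns everyone with a reactive test. The figure that the plan can produce concerns those whose reactive result the study comes to know. These groups differ by the reactive participants who never report, and such people may also be less likely to seek care.

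The study's own procedures can widen the difference. The one-week check on linkage follows a returned positive result, and the offer of a community worker follows that check (sections 8 and 9). A participant who never reports a reactive result does not reach either step.

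Linkage will be read as evidence on whether unsupervised self-testing leads people with a reactive result into care. If the figure describes only those who reported, the strategy may look safer than it is. Part of the problem is in data collection: a result not asked for at the call cannot be recovered by a later analysis plan.

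**Working it through.** **No figure to reproduce.** The protocol gives no linkage rate, upload rate or precision for linkage. Its one precision statement, ± 2–2.5% in section 14, concerns uptake: 1.96 × √(0.7 × 0.3 / 1500) = 2.32 points. That agrees with the text and has no bearing here.

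**Scale.** Section 14 plans 1000 MSM and 500 TGW, and section 3 cites prevalence of 2.3% and 5.9%. Applied in full, 1000 × 0.023 = 23 and 500 × 0.059 = 29.5, about 52 reactive participants. Fewer are to be expected, because known HIV-positive status is a non-inclusion criterion (section 1). In the gender strata one person is then worth about 1/23 = 4.3 points (MSM) or 1/29.5 = 3.4 points (TGW).

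**Bias.** Let u be the share of reactive participants who upload, Lu linkage among them and Ln linkage among the rest. All three are assumptions.

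- Linkage among all reactive participants: T = u·Lu + (1−u)·Ln.
- Only uploaders count: the estimate is Lu, and the bias is Lu − T = (1−u)(Lu − Ln).
- Linked non-uploaders found by QR code are added to numerator and denominator: the estimate is T / [u + (1−u)·Ln]. The divisor is at most 1, so the bias is upward or zero.

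Example with u = 0.7, Lu = 0.8, Ln = 0.3: T = 0.56 + 0.09 = 0.65. Upload-only gives 0.80, a bias of +15 points. With QR-found cases added, 0.65 / 0.79 = 0.823, a bias of +17.3 points.

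With Lu = 80% throughout:

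| u | Ln | All reactive (T) | Bias, upload only | Bias, QR-found added |
|---|---|---|---|---|
| 0.9 | 0% | 72% | +8 | +8.0 |
| 0.9 | 30% | 75% | +5 | +5.6 |
| 0.9 | 60% | 78% | +2 | +3.3 |
| 0.9 | 80% | 80% | 0 | +1.6 |
| 0.9 | 100% | 82% | −2 | 0 |
| 0.7 | 0% | 56% | +24 | +24.0 |
| 0.7 | 30% | 65% | +15 | +17.3 |
| 0.7 | 60% | 74% | +6 | +10.1 |
| 0.7 | 80% | 80% | 0 | +5.1 |
| 0.7 | 100% | 86% | −6 | 0 |
| 0.5 | 0% | 40% | +40 | +40.0 |
| 0.5 | 30% | 55% | +25 | +29.6 |
| 0.5 | 60% | 70% | +10 | +17.5 |
| 0.5 | 80% | 80% | 0 | +8.9 |
| 0.5 | 100% | 90% | −10 | 0 |

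**What a sensitivity range would show.** Let r be the share of delivered kits with a result, L linkage among known reactive results, and k the positivity of kits without a result relative to the observed positivity. Counting the assumed extra positives as unlinked gives rL / [r + (1−r)k]. With L = 80% and k from 1 to 3 (assumptions):

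- r = 0.9: 0.72/1.0 = 72% at k = 1, and 0.72/1.2 = 60% at k = 3.
- r = 0.7: 0.56/1.0 = 56% at k = 1, and 0.56/1.6 = 35% at k = 3.
- r = 0.5: 0.40/1.0 = 40% at k = 1, and 0.40/2.0 = 20% at k = 3.

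**The case against.** The strongest reply is that the protocol's wording is not itself wrong and that the gap is partly visible. The endpoint refers to positive self-tests, not uploaded ones. Results recorded over kits delivered will be reported by gender with a confidence interval, so a reader will see how many results are unknown. Uploading is paid (2 USD, section 9). Handling of unknown results is often left to an analysis plan, which is not at hand. This reply limits the point. It does not supply a result for a participant who never reports, and it does not add the result to what the call records.

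Four stronger readings are tempting, and the documents do not support them:

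- *Linkage is computed only among uploaders.* No section says so, and the hotline, phone and QR routes could each reveal some non-uploaders.
- *Linkage is certainly overstated.* None of u, Lu or Ln is given. If non-uploaders link more often than uploaders, for instance by going straight to a clinic, an upload-only figure is too low.
- *The percentage could exceed 100%.* That would require counting people in the numerator who are left out of the denominator, and no section proposes it.
- *Clinics hold only a partial list of codes.* Section 5 selects the sites "in order to collect information on linkage to care or prevention services for positive and negative participants, respectively", which pairs each service with a group. It does not exclude participants without a result, and no list of any kind is described. Matching all enrolled participants may already be intended.

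**Conclusion.** The point holds in a limited form. As planned, linkage is conditional on a positive result becoming known to the study, whereas the objective covers all reactive tests. No rule covers delivered kits without a result.

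Upward bias is the more likely direction, for two reasons: the active linkage support depends on a reported positive, and the QR match reveals only those non-uploaders who did reach a partner site. This is a judgement and is not established by the documents. At an assumed 80% linkage in uploaders and 50 to 90% upload, upload-only counting gives +2 to +40 points when non-uploader linkage is 0 to 60%, zero when linkage is equal, and −2 to −10 points when every non-uploader links. With QR-found cases added to both parts of the fraction, the bias is never downward. The reactive group is small enough for a few missing people to matter.

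**What to change.** In sections 7 and 14 of the protocol, with matching data-collection wording in sections 9 and 13:

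1. State which sources establish a positive result: upload, hotline or message, phone call, clinic match.
2. At the existing one-week call to non-returners, record the self-reported result as well as whether the test was done.
3. Confirm that partner sites match the QR codes of all enrolled participants, whatever their upload status.
4. Label the planned percentage *among known reactive results*, and show clinic-found non-uploaders separately.
5. Add a sensitivity range in which delivered kits with no result are given positivity from the observed value upward, for example 1 to 3 times (an assumption), and counted as unlinked. The observed value alone is not a safe lower limit, because reactive participants may be the less willing to report.

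The cascade per kit delivered may be added as a supplement. It should not replace the main figure: it is driven by prevalence (52.5/1500 = 3.5% at most on the cited prevalence) and does not answer the objective.

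The cost is one extra item at a call already planned, some wording, and a linkage result that is wider and less favourable.

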Despite Cambodia's admirable achievements the 90-90-90 targets by 2020, the HIV epidemic among key populations and, as yet, unidentified priority populations is an abiding concern. The latest available key-population data show HIV prevalence is 2.3% among men who have sex with men (MSM) and 5.9% among transgender women (TGW) (6,7). Despite this high prevalence rate, remain low the uptake of HIV testing among men who have sex with men (MSM<50%) and transgender women (TGW=39%) and consistent condom use (69% in MSM during anal sex and 38% for TGW with non-commercial sexual partners) (8). The IBBS 2019 report highlighted that about half of MSM and one third of TGW did not report any HIV testing or since more than 12 months. This suggests that undiagnosed HIV infection may persist in hard-to-reach MSM and TGW and new modality of HIV-testing approaches are hence needed to improve the uptake of HIV testing among these key populations. In addition, of those who reported HIV testing, the majority of MSM and TGW were tested at Community-based organizations (CBO) facilities (23.5% for MSM and 36.2% for TGW) and by CBO outreach workers (53.4% for MSM and 53.8% for TGW) while private facilities are poorly used for HIV (9).

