4 OBJECTIVES OF THE STUDY

Primary objective:

• Evaluate the feasibility of HIV self-testing (HIVST) delivery by a private pharmacy network among men who have sex with men (MSM) and transgender women (TGW) recruited through a classic and digital Respondent Driven Sampling method to improve HIV testing in Phnom Penh, Cambodia

Secondary objectives:

- Evaluate the acceptability and appropriateness of the strategy
- Identify barriers and facilitators
- Estimate the linkage to confirmatory testing for those with a reactive test and linkage to HIV care and ART for those with a positive confirmatory HIV test
- Estimate linkage to pre-exposure prophylaxis (PrEP) services for negative participants
- Estimate the characteristics of participants and compare to those reported in Integrated Biological and Behavioral Survey (IBBS 2019) for MSM and TGW in Cambodia
- Evaluate the adherence of participants to a 6-monthly repeated HIV testing

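### The repeat-testing proportion counts only self-tests, so it measures continued use of study kits rather than 6-monthly HIV testing, and the discontinuation event is left undefined

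*Protocol*

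**What the plan says.** The secondary objective in Section 4 is to "Evaluate the adherence of participants to a 6-monthly repeated HIV testing", and the matching endpoint in Section 7 is "Proportion of participants with 6-monthly repeated HIV testing during 18 months". Neither is limited by place or type of test. The analysis plan in Section 14 then gives the count that satisfies the endpoint: "so 4 HIVSTs during the total duration of the study".

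The data flows described are these:

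- The repeat kit is obtained with a study coupon issued after a non-reactive result (Sections 5, 8 and 9).
- Participants upload the self-test result to the study website (Section 13, Data collection).
- Participating clinics supply information on linkage to care or prevention (Section 5).
- For a missed retest, Section 9 (Loss to follow-up) says that if a "participant does not show up after receiving the reminder for 6-month HIVST, the research team will reach them by phone". It does not say what is asked or recorded. A no-show who cannot be reached is classed as lost to follow-up.

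Section 14 adds a Kaplan-Meier analysis: "The probability of discontinuation of HIV testing and its 95% confidence interval, as well as the median time to the occurrence of HIV testing discontinuation", using that method "to take into account censored data due to lost of follow-up". It gives no event definition and no time window.

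Section 3 says where people who reported testing had been tested: community-based organisation (CBO) facilities for 23.5% of MSM and 36.2% of TGW, and CBO outreach workers for 53.4% and 53.8%.

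**The concern.** The objective and endpoint are about a behaviour, testing for HIV every six months. The count in Section 14 is about a product, the self-test kit. The two coincide only if nobody retests by another route, and Section 3 describes a well-used alternative. A participant who tests with a CBO outreach worker at month 6 and leaves the coupon unused meets the objective but fails the endpoint.

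A low proportion could then be read as failure to sustain testing when part of it is a return to the usual provider. For a strategy meant to improve HIV testing, those are different conclusions. The discontinuation analysis has a related gap: it is named for HIV testing in general, but nothing says what counts as stopping or how a test taken elsewhere is handled.

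**Working it through.** **The plan's own count.** Tests at months 0, 6, 12 and 18 make 4, which agrees with Section 14. All four are self-tests, so the definition leaves no room for an outside test.

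**The alternative route.** CBO facilities plus outreach: 23.5 + 53.4 = 76.9% of MSM and 36.2 + 53.8 = 90.0% of TGW, if the two categories are exclusive. These are shares of people who reported testing. They show that another route exists. They are not the share of participants' retests that will happen outside the study.

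**Repeat-testing proportion, illustration.** The protocol gives neither a retest rate nor a share of retests made elsewhere, so both are assumed. Let r be the probability of retesting by any route in a round, e the share of those retests made outside the study, and treat the three rounds as independent.

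- Any-route proportion completing all rounds: r³
- Proportion counted from study kits only: (r(1 − e))³

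| r | any route | e = 10% | e = 20% | e = 30% |
|---|---|---|---|---|
| 0.80 | 0.80³ = 51.2% | 0.72³ = 37.3% | 0.64³ = 26.2% | 0.56³ = 17.6% |
| 0.90 | 0.90³ = 72.9% | 0.81³ = 53.1% | 0.72³ = 37.3% | 0.63³ = 25.0% |

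For any e above zero the counted proportion is below the any-route one. For comparison, the widest 95% half-width at the maximum of 1500 participants is 1.96 × √(0.25/1500) = 2.5 points, and a larger sample would not reduce the gap.

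**Discontinuation, illustration.** Take r = 0.80 and e = 20%. True discontinuation by month 18 is 1 − 0.80³ = 48.8%. The share not redeeming a kit in a round is 1 − 0.64 = 0.36. Suppose a share u of these cannot be reached and is removed from the risk set, and every reached no-show is an event (an assumption, since the protocol has no rule). Survival per round is 0.64/(1 − 0.36u), and estimated discontinuation is 1 minus its cube:

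- u = 0: 1 − 0.640³ = 73.8%
- u = 25%: 1 − (0.64/0.91)³ = 65.2%
- u = 50%: 1 − (0.64/0.82)³ = 52.5%
- u = 75%: 1 − (0.64/0.73)³ = 32.6%

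The estimate equals the truth when 1 − 0.36u = 0.80, that is u = 56%. Below that it is too high and above it too low. Two errors work against each other: outside testers counted as events push it up, and censoring people who have truly stopped pulls it down.

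**The case against.** The strongest reply is that this is a feasibility study of pharmacy self-test delivery. The six-monthly scheme offered is the repeat coupon, so adherence can naturally mean taking up those kits, and Section 14 states the count openly. Continued kit use is indeed a legitimate measure. The reply does not remove the mismatch, because the objective, the endpoint and the discontinuation outcome are all named for HIV testing.

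A reader might also infer that anyone who retests at a CBO is scored as having stopped testing in the Kaplan-Meier analysis, so that discontinuation must be overstated. The documents do not support that. Section 14 defines no event, an unreachable no-show is censored, and a reached one who reports an outside test is simply unclassified. Nor can one say that the phone call fails to ask about other tests, since its content is not given. Section 14 does use phone contact to learn whether unrecorded self-tests were performed. The e-CRF annex is not available here, so a field on testing elsewhere cannot be excluded.

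The CBO shares are also a weak guide to size. Section 3 adds that about half of MSM and one third of TGW reported no test, or none within 12 months, and those are people the strategy hopes to reach. This objection stands: the magnitude is illustrative only.

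An event definition may properly be left to a statistical analysis plan. That covers the classification rule, but a later plan cannot recover outside tests that were never recorded.

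**Conclusion.** The point holds for the repeat-testing proportion. Followed as written, it counts people who retest by another route as non-adherent. It therefore measures continued use of study kits and understates repeated HIV testing. The direction is clear whenever any retesting happens elsewhere. The size cannot be calculated from the documents. With r = 0.80, the gap runs from 51.2 − 37.3 = 13.9 points (e = 10%) to 51.2 − 17.6 = 33.6 points (e = 30%), assuming independent rounds and one common retest rate.

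For discontinuation the supportable conclusion is narrower: the event is undefined, no source for outside tests is described, and the direction of bias depends on how many no-shows are reached. Both are secondary outcomes. The change is still worth making before follow-up, because it concerns which data are collected.

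**What to change.** In the call already planned for a missed 6-month retest, ask about and record any HIV test since the last study test, with its date and place. Then report two named measures: *continued pharmacy/study HIVST* (the existing count of four) and *6-monthly HIV testing by any route*. Define the discontinuation event and its window, and do not count a reached participant who reports an outside test within the interval as having discontinued HIV testing. At minimum, if no outside tests are to be recorded, rename both Section 14 outcomes as repeat study HIVST.

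The cost is one question in an existing call and its data fields. There are limits:

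- Outside tests would be self-reported.
- They would be known only for participants who consented to phone contact and were reached.
- A question on the website at retest would miss the no-shows who matter here.

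The question also does not cure informative censoring. In the illustration, with reached outside testers no longer events, everyone reached (u = 0) gives the true 48.8%. With half of no-shows unreached, the event fraction per round is 0.20 × 0.5/0.82 = 0.122, and the estimate is 1 − (0.72/0.82)³ = 32.3%. Both versions should therefore be shown, with the number not reached at each round.
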